9.4. Table 1. Tolerance assessment scale

| Bioven | Page 64 |
|----------------------------|--------------------------------|
| Trial Code: 2021-BV-ITP-BP | Version 1.4 from July 03, 2023 |

Signs and symptoms, which are based on general pathology, if possible, should be noted as one complex phenomenon. If the diagnosis is known, it should be registered as the name of the AE. If the diagnosis is unknown, each complaint and symptom should be recorded as a separate AE.

The information to be recorded includes the type of phenomenon, the date of development of the AE, the researcher's assessment of the severity and relationship of the AE with the study drug, the date of termination (decision) of the AE, the severity of the AE, the measures taken and the outcome of the AE.

All the AEs should be monitored until they are adequately addressed.

During and after the subject's participation in the study, the researcher (medical institution) must ensure that the subject is provided with the necessary medical care in the event of any study-related adverse events, including clinically significant changes in laboratory parameters. The researcher (medical institution) is obliged to inform the research subject about intercurrent diseases that require medical care, which became known to the researcher.

9.5. Assessment of the severity of AE

The severity (expressiveness) of AEs indicates the extent to which AEs affect the patient's daily activities. The severity of the AE will be determined according to the NCI CTCAE criteria developed by the US National Cancer Institute (version 5.0) (in each paragraph a semicolon means "or") Table 2.

| Severity 1 | Easy; no symptoms or minor symptoms; only clinical or diagnostic | |
|------------|--|--|
| | observations; no intervention is required | |
| Severity 2 | Moderate; requires minimal, local or non-invasive intervention (eg, | |
| - | tamponade, cauterization); the restriction corresponds to the Social Daily | |
| | Activities (SDA), Instrumental Activities of Daily Living (ADL *) | |
| Severity 3 | Severe or clinically significant but not life-threatening; hospitalization | |
| - | or continuation of hospitalization is required; restriction of vital activity; | |
| | Self Care Activities of Daily Living (ADL **) | |
| Severity 4 | Life-threatening condition; immediate intervention is required | |
| Severity 5 | Death associated with AE | |

9.6. Table 2. The severity of NOT according to NCI CTCAE (version 5.0)

Daily activity (ADL):

* Social daily activities (SDA) include cooking, buying food or clothing, using the phone, handling money, etc.

** Self-care (SC) includes taking a bath, dressing and undressing, eating alone, using the toilet, taking medication and not being bedridden.

The terms "serious" and "severe" are not synonymous. Severe AE (Grade 3 or 4) should not always be considered serious. For example, leukocyte counts between 1000 and 2000 / mm3 should be considered grade 3 (severe), but such may not be considered severe. The benchmark for submitting information to regulators is the severity (not the expressiveness) of the AE.

9.7. Assessment of the causal relationship of AE with the study drug

In assessing the cause-and-effect relationship, the investigator should consider the possible etiology of the observed AE / AR phenomenon, which may be due to the study drug, concomitant

| Bioven | Page 65 |
|----------------------------|--------------------------------|
| Trial Code: 2021-BV-ITP-BP | Version 1.4 from July 03, 2023 |

medications, underlying disease, comorbidities, study procedures, and other reasons. For all possible reasons, the researcher must determine the one that has the most likely causal relationship with the phenomenon. When assessing the causal relationship in the case of a serious AR, the report must provide a justification for this assessment. The justification should include all available evidence confirming the assessment, including the results of laboratory tests and other diagnostic procedures.

- The causal relationship is determined. The clinical phenomenon and / or changes in laboratory parameters are time-related to the drug and cannot be explained by comorbidities, other drugs or chemicals. The response to drug withdrawal should be clinically accurate. The phenomenon was confirmed by conducting, if necessary, a provocative test procedure.
- Probable causation.Clinical events and / or changes in laboratory parameters related to
 the time of administration of the drug, which can hardly be explained by concomitant
 disease or the use of other drugs or chemical compounds, in the presence of a clinically
 pronounced response to drug withdrawal.
- A causal relationship is possible. Clinical phenomenon and / or changes in laboratory
 parameters related to the time associated with the drug, but which can be explained by
 the presence of comorbidities or other drugs and chemicals. Information on drug response
 may be missing or unclear.
- Unlikely causation.Clinical events and / or changes in laboratory parameters may be related in time to the administration of the drug, but other drugs, chemicals or comorbidities provide a more plausible explanation for the phenomenon.
- No connection. The clinical phenomenon and / or changes in laboratory parameters are certainly not related to the use of the drug due to the unreasonable temporal relationship between the drug and AR and / or the improbability of such a relationship.

9.8. Categories of consequences of AE and their definitions

Measures taken:

- Without treatment;
- □ Cancellation of the suspected drug;
- □ Reducing the dose of the suspected drug;
- □ Cancellation of concomitant treatment;
- \Box Use of drug therapy;
- □ Non-drug therapy (including surgery).

The phenomenon passed without consequences -there are no symptoms, and the patient is not treated to eliminate this AR.

Stabilization of the state -the result of AR is classified as stabilization of the state according to the researcher.

The phenomenon passed with consequences -the phenomenon was curtailed, but its consequences remained; as a result of AR the patient has a temporary or permanent disability / incapacity; any AR that have passed with consequences are classified as serious AR.

The phenomenon has not yet passed -symptoms persist.

Death of the patient.

The result is unknown.

| Bioven | Page 66 |
|----------------------------|--------------------------------|
| Trial Code: 2021-BV-ITP-BP | Version 1.4 from July 03, 2023 |

9.9. Reports of SAE

In the case of any SAE, the Study Sponsor must be notified within 24 hours of the researcher first learning about the SAE. During the development of SAE, the researcher fills in the SAE registration form and determines whether it is associated with the study drug and sends by fax or e-mail the completed form to the Sponsor of the study. The original SAE form and the fax confirmation letter must be kept. The fact of SAE should be recorded in the IRF. The sponsor has the right to urgently request from the researcher additional information about SAE for reporting to health authorities.

After the initial urgent notification, a detailed written notification must be submitted as soon as possible. Primary and subsequent reports should identify the subjects of the study by the unique code assigned to them, and not by the names of the subjects, personal identification numbers and (or) addresses.

In case of hospitalization of the patient in connection with the development of SAE, it is necessary to send as soon as possible fax or e-mail to the Sponsor of the study a copy of the hospital discharge.

The sponsor of the study or his authorized representative is responsible for notifying by telephone or fax of unforeseen or life-threatening SAEs related to the use of the study drug (in the form of urgent reports) to the relevant authorities and competent authorities within 7 calendar days obtaining information about SAE. The sponsor of the study drug to the appropriate authorities, researchers and the local ethics committee by providing a written safety report within 15 calendar days of receiving the information about SAE.

In Ukraine, the sponsor shall immediately register and within 7 calendar days from the moment he became aware of it, inform the SEC of the Ministry of Health of Ukraine and the Ethics Commission of all suspected unforeseen serious adverse reactions to the investigational medicinal product that resulted in death or threat for the life of the subject. Additional information on this subject is provided by the SEC of the Ministry of Health of Ukraine and the Ethics Commission within the next 8 calendar days. The notification of a suspected unforeseen serious adverse reaction must be made in accordance with the order of the Ministry of Health of Ukraine $N_{\rm D}$ 690 of 23.09.2009, as amended.

In addition to the death notification, the researcher shall provide any additional information at the request of the regulatory authority (autopsy report and final medical reports after their proper preparation in accordance with the legislation of the country where the study is conducted - Ukraine).

9.10. Requirements for reporting after completion of the study drug

If the Researcher receives information about any AR that has occurred at any time after the patient has taken the study drug, and there are sufficient grounds to suggest a connection between this phenomenon and the study drug, the Researcher must notify Sponsor.

9.11. Contraception and pregnancy

Prior to the start of the study, men and women of childbearing potential will be informed of the importance of contraception during the study and within 3 weeks of completion. Reliable methods of contraception include: surgical sterilization, double barrier method of contraception, local contraception. The study will also be open to women who do not use acceptable methods of

| Bioven | Page 67 |
|----------------------------|--------------------------------|
| Trial Code: 2021-BV-ITP-BP | Version 1.4 from July 03, 2023 |

contraception if they are declared unfit for childbirth: women who have undergone a hysterectomy (removal of the uterus) or tubal ligation, women with a clinical diagnosis of infertility, and women who are in the menopausal period more than 1 year (absence of menstruation for at least 12 months).

9.12. The period of time during which the collection of information about pregnancy is required.

It is necessary to collect information on the course of any pregnancy throughout the clinical trial, starting with the first dose of the study drug.

9.13. Actions to be taken in case of pregnancy.

The researcher will collect information about the pregnancy of any patient who became pregnant during the study. The researcher will record information about the onset of pregnancy and pass the information to the Sponsor of the study. The procedure for reporting a pregnancy is similar to the procedure for reporting a serious adverse event.

Pregnancy is not considered as a AE, but any complication of pregnancy or planned termination of pregnancy on medical grounds will be registered as AE, and such a patient will be monitored. Spontaneous abortion is always considered a AE and should also be reported to the Sponsor. In addition, the Sponsor must be notified of any AE that has occurred as a result of a post-study pregnancy that is considered by the investigator to be reasonably related to the study drug being studied. Although the researcher is not required to actively seek this information from former study participants, he / she may learn about AE spontaneously from the participants' own reports. Patients who become pregnant will be excluded from the study.

10 STATISTICS

10.1 Content of statistical analysis

The null hypothesis for the primary efficacy endpoint H0: $p-p_0 \leq \delta$, where clinical effectiveness p is the proportion of patients who responded to therapy with the study drug BIOVEN; p_0 - proportion of patients responding to therapy according to literature data: δ - the limit of the difference of proportions without clinical significance. An alternative hypothesis H1: $p-p_0 > \delta$ («non-inferiority study» according to the guideline EMA «Points to consider on switching between superiority and non-inferiority» CPMP/EWP/482/99, London, 27 July 2000 Ta EMA "ICH Topic E 9 Statistical Principles for Clinical Trials" CPMP/ICH/363/96).

According to the EU recommendations on clinical studies of immunoglobulin normal for intravenous administration (Guideline on the clinical investigation of human normal immunoglobulin for intravenous administration (IVIg), EMA/CHMP/BPWP/94033/2007 rev. 3, 28 June 2018) the obtained results will be compared with literature data.

To test the null hypothesis, a two-tailed test will be used, based on the principles of estimating a 95% confidence interval for the difference in proportions and comparing it with the lower limit of equivalence (at a significance level of α 5%). For non-inferiority research, the null hypothesis is rejected if the conditions are met:

$$\sqrt{n(p-p_0-\delta) / p^{(1-p^{-})} > z_{\alpha/2}}$$

or
 $(p-p_0-\delta) / \sqrt{(\frac{p(1-p)}{n} + \frac{p_0(1-p_0)}{n_0})} > z_{\alpha/2}$

Confidence intervals of the difference will be calculated according to the generally accepted Wald method:

$$(p_1 - p_2) \pm z_{\alpha/2}^* \sqrt{(\frac{p_1(1 - p_1)}{n_1} + \frac{p_2(1 - p_2)}{n_2})}$$

The number of patients for the portion taken from literature sources is taken from the 2020 publication and will be 82 [Parodi E, Russo G, Farruggia P, Notarangelo LD, Giraudo MT, Nardi M, et al. Management strategies for newly diagnosed immune thrombocytopenia in Italian AIEOP Centres: do we overtreat? Data from a multicentre, prospective cohort study. Blood Transfus. 2020;18(5):396.]

Methods of descriptive statistics (for categorical variables - number and part in %, for quantitative variables - n, arithmetic mean, median, standard deviation, minimum and maximum), including construction of graphs and charts, methods of interval estimation (calculate of 95% confidence intervals for proportions and differences of fractions).

For variables that are "time to event" survival curves will be constructed in each group using the Kaplan-Meier method, median survival will be estimated, and group comparisons will be made using the log-rank test. If the survival curves intersect, then Cox regression will be used to compare the groups according to these variables.

| Bioven | Page 69 |
|----------------------------|--------------------------------|
| Trial Code: 2021-BV-ITP-BP | Version 1.4 from July 03, 2023 |

To evaluate the significance in the dynamics in the case of evaluating the parameter on two visits (before and after):

- To assess the dynamics of quantitative variables, the Student's test for paired data or the Wilcoxon signed rank test will be applied, depending on the results of testing the normality of the distribution of differences [after - before] using the Shapiro-Wilk test.

- To assess the dynamics of categorical variables in groups, the McNemar criterion or the criterion of homogeneity of marginal frequencies will be applied, depending on the number of categories.

- To assess the statistical significance of differences in categorical variables in unrelated groups, Pearson's chi-square or Fisher's exact test will be applied (depending on the frequency distribution in table 2*2).

To evaluate the dynamics in the case of measuring variables on more than two visits, methods of univariate analysis of variance (ANOVA) will be used followed by contrast analysis (simple contrasts) or a posteriori analysis using Tukey's test. Analysis of covariance (ANCOVA) will be used to compare those variables for which the data were heterogeneous at baseline.

To verify the prerequisites for the application of variance and covariance analyses, a check of the normality of the data distribution and their residuals will be performed using the Shapiro-Wilk test. If the residuals are not normally distributed, or if the data fail the normality test, an appropriate rank analysis will be performed.

For the Shapiro-Wilk test, the significance level will be 0.01, and for other criteria - 0.05. In the event of the effect of multiple comparisons, an adjustment of the level of significance will be applied using the Holm method or the Benjamini-Hochberg method.

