Null hypothesis H0: $p-p0 \le \delta$, where clinical efficacy p- is the part of patients who responded to therapy with BIOVEN 10%; p_0 – part of patients responding to therapy according to literature data; δ is the limit of the difference of parts without clinical significance. Alternative hypothesis H1: $p-p0 > \delta$

The non-inferiority assessment is performed according to the EMA guideline "Points to consider on switching between superiority and non-inferiority" CPMP/EWP/482/99, London, July 27, 2000, and the EMA guideline "ICH Topic E 9 Statistical Principles for Clinical Trials" CPMP/ICH/363/96.

To test the null hypothesis, a two-tailed test will be used, based on the principles of estimating a 95% confidence interval for the difference in proportions and comparing it with the lower limit of equivalence (at a significance level of α 5%). For non-inferiority research, the null hypothesis is rejected if the following conditions are met:

$$\frac{\sqrt{n(p-p_0-\delta)} / p^{(1-p)} > z_{\alpha/2}}{(p-p_0-\delta) / \left[\frac{p(1-p)}{n} + \frac{p_0(1-p_0)}{n_0} \right] > z_{\alpha/2}}$$

The sample size n in a group when comparing proportions for a study with no less efficiency is calculated by the formula (Chow, S. C., Wang, H., & Shao, J. (2007). Sample size calculations in clinical research. Chapman and Hall/CRC .):

 $n=(Z_{a/2}+Z_{b/2})^2 \times (p \times (1-p))/(p-p_0-\delta)^2$

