In accordance with the EMA recommendations on the clinical investigation of human normal immunoglobulin for intravenous administration (*Guideline on the clinical investigation of human normal immunoglobulin for intravenous administration (IVIg), EMA/CHMP/BPWP/94033/2007 rev. 4, 16 Dec 2021*) the obtained results will be compared with literature data The conclusion of non-inferiority of the drug Bioven, solution for infusions 10%, in the treatment of chronic immune thrombocytopenia, will be made according to the main efficacy variable using an approach based on confidence intervals.

To do this, the calculated limits of the 95% confidence interval (CI) for the difference in the percentage of positive results according to the main variable ("the drug is effective") for the studied group must be compared with the limit of the non-inferiority zone - effectiveness that is not inferior (-25%) to the calculated based on data for comparison. If the lower limit of the CI is greater than the lower limit of the non-inferiority zone (non-inferiority), then it will be considered that the study drug is not inferior in effectiveness compared to literature data. A detailed description of statistical analysis is provided in the corresponding section of this Protocol.

Examination methods:

Examination methods are performed according to the schedule of events provided in the relevant section of the Protocol of this clinical trial.

- Collection and recording of demographic data;
- Collection and recording of medical history;
- Verification of ITP diagnosis (according to primary documentation);
- Recording information about previous ITP therapy (dose/schedule, duration, response (if any), and time interval since the last administration);
- Recording information about symptomatic therapy and medication intake for the treatment of concomitant diseases;
- Transfusion history;
- History of allergies;
- Determination of body weight;
- Objective physical examination with mandatory assessment of the severity of hemorrhagic syndrome;

| Bioven | |
|----------------------------|--|
| Trial Code: 2021-BV-ITP-BP | |

| - Measurement of vital signs (blood pressure, heart rate, respiratory rate, body | |
|---|--|
| temperature); | |
| - Biomaterials sampling for laboratory tests is carried out at collection points or by mobile | |
| team of the Central Laboratory designated by the Sponsor: | |
| - Blood test for HIV and RW, PCR EBV, CMV; | |

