4. STUDY DESIGN

4.1. Model description, number of patients, groups

Study design: open-label, multicenter, international, non-randomized, non-controlled, singlegroup study evaluating the efficacy, safety and tolerability of Bioven, 10% solution for infusion.

Number of patients: The number of subjects in Ukraine and worldwide is 40 patients: men and women aged 18-65 years with a confirmed diagnosis of chronic primary immune thrombocytopenia (at least 12 months from the date of diagnosis). In Ukraine, no more than 36 patients will be enrolled.

Groups: This study does not provide for the division of patients into groups. Patients who have been screened and meet the inclusion criteria, who do not have non-inclusion (exclusion) criteria and those who have signed the Informed Consent Form (ICF), are included in the study, and receive the study drug (SD).

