scheme is recommended by the EMA and this Protocol, the total number of patients in the group is 82, the effectiveness of the use of IVIG in the treatment of ITP is indicated - 78% [Parodi E, Russo G, Farruggia P, Notarangelo LD, Giraudo MT, Nardi M, et al. Management strategies for newly diagnosed immune thrombocytopenia in Italian AIEOP Centres: do we overtreat? Data from a multicentre, prospective cohort study. Blood Transfus. 2020;18(5):396.]. According to our data and data from the literature, immunoglobulin belongs to drugs with a highly variable efficiency of 20-25%. Therefore, for a non-inferiority study, we consider it appropriate to set δ (the limit of the difference in efficiency between the obtained and expected results) at the level of -25%.

Thus, for a significance level of 5% and a statistical power of 80%, the effectiveness of the drug in the comparison model reaches 78%, the limit of the difference in specific weights (difference in effectiveness) without clinical significance δ is - 0.25. Then the calculation of the minimum sample size will look like this:

 $n = (1,96+1,28)2 \times (0,78 \times (1-0,78) / (0,78 - 0,78 + 0,25)^2 = 29$

Considering the risk of dropping out of patients for various reasons (20%), 36 patients will be included in the study.

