10.3.7. Conclusion on non-inferiority effectiveness

In accordance with EMA recommendations for clinical studies of immunoglobulin normal for intravenous administration (*Guideline on the clinical investigation of human normal immunoglobulin for intravenous administration (IVIg)*, *EMA/CHMP/BPWP/94033/2007 rev. 4, 16 December 2021)* the obtained results will be compared with literature data The conclusion of non-inferiority of the drug Bioven, solution for infusions 10%, in the treatment of chronic immune thrombocytopenia, will be made according to the main efficacy variable using an approach based on confidence intervals. To do this, the calculated limits of the 95% confidence interval (CI) for the difference in the

percentage of positive results according to the main variable ("the drug is effective") for the studied group must be compared with the limit of the non-inferiority zone - effectiveness that is not inferior (-25%) to the calculated based on data for comparison. If the lower limit of the CI is greater than the

| Bioven | Page 74 |
|----------------------------|--------------------------------|
| Trial Code: 2021-BV-ITP-BP | Version 1.4 from July 03, 2023 |

lower limit of the non-inferiority zone (non-inferiority), then it will be considered that the study drug is not inferior in effectiveness compared to literature data.

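### Section 10.1 accepts either of two unequal non-inferiority tests, the conclusion rule uses only one, and the sample size is derived from the other; the total is 36 in 10.2 but 40 in 4.1

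*Combined protocol and SAP*

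**What the plan says.** - **Rejection rule.** Section 10.1 says "For non-inferiority research, the null hypothesis is rejected if the conditions are met" and then lists two inequalities separated by *or*. The first has no term for the literature group. The second has p0(1-p0)/n0 in its standard error. The synopsis (Sample size calculation) lists both under "For non-inferiority research, the null hypothesis is rejected if the following conditions are met", and no *or* is visible in the extracted text.
- **Confidence interval.** The only interval formula for the difference is the two-sample Wald interval in 10.1, with the literature group set at 82.
- **Conclusion.** Section 10.3.7 says that the conclusion "will be made according to the main efficacy variable using an approach based on confidence intervals". The synopsis gives the same rule: "If the lower limit of the CI is greater than the lower limit of the non-inferiority zone (non-inferiority), then it will be considered" non-inferior.
- **Sample size.** Section 10.2 works "for a significance level of 5% and a statistical power of 80" per cent, with the one-sample variance p(1-p), a term printed as Z_{b/2} and the value 1.28. It obtains 29.
- **Total.** After 20% dropout, 10.2 and the synopsis sample-size text say "36 patients will be included in the study". Section 4.1 says "The number of subjects in Ukraine and worldwide is 40 patients" and "In Ukraine, no more than 36 patients will be enrolled".

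**The concern.** The primary conclusion should rest on one rule, and the sample size should come from that rule. Here a stated rejection rule and the stated conclusion rule can give opposite answers on the same data. The first inequality treats the 78% literature rate as known exactly. The interval beside it treats that rate as an estimate from 82 patients.

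The trial is open-label and single-arm, so at a borderline responder count the choice between rules could be made with the result in view. The sample-size text has the same fault: it uses the variance of the test that does not govern and a power label that does not match that test. The two totals leave the reader unsure how many patients the power statement refers to.

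**Working it through.** **Inputs.** p = p0 = 0.78, margin -0.25, two-sided 5% (z = 1.96, so 2.5% in the non-inferiority direction), stated power 80%, value used 1.28, dropout 20% (all 10.2); n0 = 82 (10.1). The typesetting of the first inequality is garbled. I read it as √n(p - p0 - δ)/√[p(1-p)] > z, the form that matches the formula in 10.2. Note p(1-p) = 0.78 × 0.22 = 0.1716 and 0.25² = 0.0625.

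**1. The plan's own figure.** (1.96 + 1.28)² × 0.1716 / 0.0625 = 28.8, so 29. This reproduces. 29/0.8 = 36.25, given as 36 (37 if rounded up).

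**2. What 1.28 means.** It is the normal quantile for 90%. It follows from halving b = 0.20, but rejection here is in one direction only, so b should not be halved. For the one-sample test at 80%: (1.96 + 0.84)² × 0.1716 / 0.0625 = 21.5, so 22.

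**3. Size under the interval rule.** Solve 0.1716/n + 0.1716/82 = 0.0625/(1.96 + 0.84)². The result is n = 0.1716/(0.007972 - 0.002093) = 29.2, so 30 evaluable, and 30/0.8 = 37.5, so 38 enrolled. By the same normal approximation, n = 29 gives 79.8% and n = 32 (40 less 20%) gives 82.5%.

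**4. The *or*.** The first standard error omits a positive term, so every count that passes the second test also passes the first. *Or* is therefore the first test alone. If the synopsis list is read as requiring both, it is the second test alone.

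**5. A count where they disagree.** For 25/36 = 0.694 the difference from 0.78 is -0.086.
- First rule: SE = √(0.694 × 0.306/36) = 0.0768; lower limit -0.086 - 1.96 × 0.0768 = -0.236, above -0.25, pass.
- Interval rule: SE = √(0.005894 + 0.002093) = 0.0894; lower limit -0.261, below -0.25, fail.

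This count has probability 7.0% if the true rate is 0.78 and 14.3% if it is 0.70.

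**6. Responders needed and exact one-sided error at a true rate of 0.53, with p0 fixed at 0.78.**

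| Evaluable n | Needed, first rule | Needed, interval rule | Error, first rule | Error, interval rule |
|---|---|---|---|---|
| 29 | 21 | 21 | 2.65% | 2.65% |
| 30 | 21 | 22 | 4.5% | 1.9% |
| 32 | 23 | 23 | 2.3% | 2.3% |
| 36 | 25 | 26 | 3.4% | 1.5% |
| 40 | 28 | 28 | 2.2% | 2.2% |

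From 28 to 40 the rules differ, always by one responder, at every size except 29, 32, 37 and 40: 9 sizes of 13.

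**7. Error when the literature rate is itself an estimate.** With the literature count drawn as Bin(82, 0.78) and a true rate of 0.53, the one-sided error is 4.7-5.3% for the *or* rule and 2.8-3.1% for the interval rule, at every n from 28 to 40.

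**The case against.** **The governing rule is clear enough.** Section 10.1 describes its test as based on a 95% interval, gives one interval formula, and 10.3.7 concludes by interval. This makes the interval the natural rule to keep. It does not remove the *or*, which is printed as a rejection rule and gives a different answer at most sizes.

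**The first inequality is garbled, and the *or* missing from the synopsis may be an extraction fault.** Its exact form is a reconstruction. That it has no n0 term is legible, however, and the formula in 10.2 has the same structure. Nothing here depends on the synopsis reading.

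**The effect is small.** The gap is never more than one responder, and the rules agree at 29 and at 32, the number left from 40 after 20% dropout. That is true. But efficacy is analysed in the per-protocol set, whose size is not known in advance.

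**The 80% label is about right.** For the interval rule it is (79.8% at 29). The agreement is a coincidence of two departures, the omitted variance term and the larger quantile.

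**The error figures of 4.7-5.3% need a model for the literature rate.** They do, and under that model the interval rule also exceeds 2.5%. With p0 fixed, part of the excess is discreteness. The same model gives 78.3% power at 30 evaluable and first reaches 80% at 32 (80.4%), so 40 enrolled is better supported than 38.

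**Conclusion.** The concern holds. The stated rejection rule and the stated conclusion rule can disagree, by one responder, at 9 of the 13 evaluable sizes from 28 to 40. If the literature rate is treated as an estimate from 82 patients, the *or* rule roughly doubles the nominal 2.5% one-sided error, while the interval rule stays near 3%.

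The 29 in 10.2 is a 90% figure for the one-sample test, carrying an 80% label. For the interval rule it gives 79.8%, so there is no material loss of power; the fault is in the derivation. The totals of 36 and 40 conflict and are not reconciled anywhere.

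This rests on the one-sample reading of the garbled inequality, on p = p0 = 0.78 and on n0 = 82. It should be fixed before analysis, but it does not threaten the feasibility of the trial.

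**What to change.** 1. In 10.1 and the synopsis, delete the first inequality; in 10.1 also delete the *or*. Make the two-sided 95% interval with n0 = 82, compared with -25%, the only decision rule.
2. In 10.2 and the synopsis, replace the formula by one with both variance terms and Z_b = 0.84. This gives 29.2, so 30 evaluable and 38 enrolled at 20% dropout.
3. Give 40 as the total in 10.2 and the synopsis sample-size text. Keep 36 only as the maximum for Ukraine.
4. State the power for the 32 evaluable patients expected from 40: 82.5% by normal approximation. For information, exact power is 85.3% with the literature rate fixed and 80.4% with the literature count varying.

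The cost is wording only. No patients are needed beyond the 40 already planned. Relative to the one-sample test, the interval rule asks for one more responder at 9 of the 13 sizes, which 10.3.7 already requires.
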